**Table 3 Trial Treatments**

Drug	Dose	Dose Frequency	Route of Administration	Regimen/Treatment Period/Vaccination Regimen	Use
Pembrolizumab	200 mg	Q3W	IV infusion	Day 1 of each cycle	Experimental
Normal Saline	NA	Q3W	IV infusion	Day 1 of each cycle	Placebo
Cisplatin*	80 mg/m 	Q3W	IV infusion	Day 1 of each cycle	Comparator regimen and combination agent
5-FU**	800 mg/m 	Q3W	IV infusion	Continuous Days 1-5 (120 hours) of each cycle	Comparator regimen and combination agent
Capecitabine**	1000 mg/m  BID	Q3W	Oral	D1-14	Comparator regimen and combination agent

* Duration of cisplatin treatment may be capped at 6 cycles as per local country guidelines, however treatment with 5-FU/capecitabine may continue per protocol.
 
**Although use of 5-FU infusion is preferred, capecitabine 1000 mg/m^2 bid D1-14 Q3W may be permitted according to local guideline. Investigator decision regarding the type of comparator used (5-FU or capecitabine) should be determined prior to randomization in the trial.
					

All trial treatments will be administered on an out-patient basis.

Trial treatment should begin on the day of randomization or as close as possible to the date on which the subject is allocated/assigned.

All supplies indicated in [Table 3](#) above will be provided centrally by the Sponsor or locally by the trial site, subsidiary or designee, depending on local country operational or regulatory requirements.

For any commercially available product that is provided by the trial site, subsidiary or designee every attempt will be made to source these supplies from a single lot/batch number. The trial site will be responsible for recording the lot number, manufacturer and expiry date of any locally purchased product.

The investigator shall take responsibility for and shall take all steps to maintain appropriate records and ensure appropriate supply, storage, handling, distribution and usage of trial treatments in accordance with the protocol and any applicable laws and regulations.

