### **5.2.1.2 Dose Modification**

If appropriate, the Investigator may attribute each toxicity event to cisplatin, 5-FU (or capecitabine) or pembrolizumab alone in the combination arms and use a stepwise dose reduction according to [Table 4](#) to [Table 8](#). For individual subjects requiring a dose modification, treatment for each new cycle may be delayed if the scheduled off-drug periods are not adequate to allow for recovery to Grade  $\leq 1$  or the baseline status of the subject.

Pembrolizumab/placebo dose reductions are not permitted. Pembrolizumab/placebo treatment may be interrupted or discontinued due to toxicity. If a dose reduction for toxicity occurs with any agent, the dose may not be re-escalated. Subjects can have a maximum of 2 dose modifications (if applicable) to each of the components of study therapy throughout the course of the study for toxicities. If a subject experiences several toxicities and there are conflicting recommendations, please follow the most conservative dose adjustment recommended (dose reduction appropriate to the most severe toxicity). Subjects who require a 3rd dose modification to any particular component will have that agent discontinued.

Reduction of one chemotherapy agent and not the other agent is appropriate if, in the opinion of the Investigator, the toxicity is clearly related to one of the treatments. If, in the opinion of the Investigator, the toxicity is related to the combination of both chemotherapy agents, both drugs should be reduced according to recommended dose modifications. If the toxicity is related to the combination of three agents, chemotherapy should be reduced, interrupted or discontinued; pembrolizumab/placebo should be interrupted or discontinued according to the recommended dose modifications. If a decision is made to discontinue combination chemotherapy due to treatment related AE(s), the subject can be unblinded after discussion with sponsor to identify study treatment. Subjects receiving pembrolizumab therapy may have both the cisplatin and 5-FU or capecitabine discontinued and continue on pembrolizumab alone, while subjects on combination with placebo (arm 3) may discontinue from study treatment.

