#### 5.2.1.2.1 Dose Modification and Toxicity Management Guidelines for Pembrolizumab/Placebo

##### **Dose modification and toxicity management for immune-related AEs associated with pembrolizumab**

Adverse events associated with pembrolizumab exposure may represent an immunologic aetiology. These immune-related AEs (irAEs) may occur shortly after the first dose or several months after the last dose of pembrolizumab treatment and may affect more than one body system simultaneously. Therefore, early recognition and initiation of treatment is critical to reduce complications. Based on existing clinical trial data, most irAEs were reversible and could be managed with interruptions of pembrolizumab, administration of corticosteroids and/or other supportive care. For suspected irAEs, ensure adequate evaluation to confirm aetiology or exclude other causes. Additional procedures or tests such as bronchoscopy, endoscopy, skin biopsy may be included as part of the evaluation. Based on the severity of irAEs, withhold or permanently discontinue pembrolizumab and administer corticosteroids. Dose modification and toxicity management guidelines, for irAEs associated with pembrolizumab are provided in [Table 5](#).

Table 5 Dose Modification and Toxicity Management Guidelines for Immune-related AEs Associated With pembrolizumab

General instructions:				

 
1. Corticosteroid taper should be initiated upon AE improving to Grade 1 or less and continue to taper over at least 4 weeks.
 
2. For situations where pembrolizumab has been withheld, pembrolizumab can be resumed after AE has been reduced to Grade 1 or 0 and corticosteroid has been tapered. Pembrolizumab should be permanently discontinued if AE does not resolve within 12 weeks of last dose or corticosteroids cannot be reduced to <math>\leq 10</math> mg prednisone or equivalent per day within 12 weeks.
 
3. For severe and life-threatening irAEs, IV corticosteroid should be initiated first followed by oral steroid. Other immunosuppressive treatment should be initiated if irAEs cannot be controlled by corticosteroids.
 
				
Immune-related AEs	Toxicity grade or conditions (CTCAEv4.0)	Action taken to pembrolizumab	irAE management with corticosteroid and/or other therapies	Monitor and follow-up

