Pneumonitis	Grade 2	Withhold	
 
• Administer corticosteroids (initial dose of 1-2 mg/kg prednisone or equivalent) followed by taper
 
	
 
• Monitor subjects for signs and symptoms of pneumonitis
 
• Evaluate subjects with suspected pneumonitis with radiographic imaging and initiate corticosteroid treatment
 
• Add prophylactic antibiotics for opportunistic infections
 

	Grade 3 or 4, or recurrent Grade 2	Permanently discontinue	
 
•
 
	
Diarrhoea / Colitis	Grade 2 or 3	Withhold	
 
• Administer corticosteroids (initial dose of 1-2 mg/kg prednisone or equivalent) followed by taper
 
	
 
• Monitor subjects for signs and symptoms of enterocolitis (ie, diarrhoea, abdominal pain, blood or mucus in stool with or without fever) and of bowel perforation (ie, peritoneal signs and ileus).
 
• Subjects with <math>\geq</math> Grade 2 diarrhoea suspecting colitis should consider GI consultation and performing endoscopy to rule out colitis.
 
• Subjects with diarrhoea/colitis should be advised to drink liberal quantities of clear fluids. If sufficient oral fluid intake is not feasible, fluid and electrolytes should be substituted via IV infusion.
 

	Grade 4	Permanently discontinue		

Immune-related AEs	Toxicity grade or conditions (CTCAEv4.0)	Action taken to pembrolizumab	irAE management with corticosteroid and/or other therapies	Monitor and follow-up
AST / ALT elevation or Increased bilirubin	Grade 2	Withhold	
 
Administer corticosteroids (initial dose of 0.5- 1 mg/kg prednisone or equivalent) followed by taper
 
	
 
Monitor with liver function tests (consider weekly or more frequently until liver enzyme value returned to baseline or is stable)
 

	Grade 3 or 4	Permanently discontinue	
 
Administer corticosteroids (initial dose of 1-2 mg/kg prednisone or equivalent) followed by taper
 
	

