
Grade 2            Requires infusion interruption but responds promptly to symptomatic treatment (eg, antihistamines, NSAIDs, narcotics, IV fluids); prophylactic medications indicated for ≤24 hrs.
	
Stop Infusion and monitor symptoms.            Additional appropriate medical therapy may include but is not limited to:            IV fluids            Antihistamines            NSAIDs            Acetaminophen            Narcotics
 
Increase monitoring of vital signs as medically indicated until the subject is deemed medically stable in the opinion of the investigator.
 
If symptoms resolve within one hour of stopping drug infusion, the infusion may be restarted at 50% of the original infusion rate (eg, from 100 mL/hr to 50 mL/hr). Otherwise dosing will be held until symptoms resolve and the subject should be premedicated for the next scheduled dose.
 
Subjects who develop Grade 2 toxicity despite adequate premedication should be permanently discontinued from further trial treatment administration.
	
Subject may be premedicated 1.5h (± 30 minutes) prior to infusion of pembrolizumab (MK-3475) with:
 
Diphenhydramine 50 mg po (or equivalent dose of antihistamine).
 
Acetaminophen 500-1000 mg po (or equivalent dose of antipyretic).

Grades 3 or 4            Grade 3:            Prolonged (ie, not rapidly responsive to symptomatic medication and/or brief interruption of infusion); recurrence of symptoms following initial improvement; hospitalization indicated for other clinical sequelae (eg, renal impairment, pulmonary infiltrates)            Grade 4:            Life-threatening; pressor or ventilator support indicated
	
Stop Infusion.            Additional appropriate medical therapy may include but is not limited to:            IV fluids            Antihistamines            NSAIDs            Acetaminophen            Narcotics            Oxygen            Pressors            Corticosteroids            Epinephrine
 
Increase monitoring of vital signs as medically indicated until the subject is deemed medically stable in the opinion of the investigator.
 
Hospitalization may be indicated.
 
Subject is permanently discontinued from further trial treatment administration.
	
No subsequent dosing

Appropriate resuscitation equipment should be available in the room and a physician readily available during the period of drug administration.
		

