### **5.8 Subject Withdrawal/Discontinuation Criteria**

#### **5.8.1 Discontinuation of Treatment**

Discontinuation of treatment does not represent withdrawal from the trial.

As certain data on clinical events beyond treatment discontinuation may be important to the study, they must be collected through the subject's last scheduled follow-up, even if the subject has discontinued treatment. Therefore, all subjects who discontinue trial treatment prior to completion of the trial will still continue to participate in the trial as specified in Section 6.0 - Trial Flow Chart and Section 7.1.5.3 – Post-Treatment Visits.

Subjects may discontinue treatment at any time for any reason or be dropped from treatment at the discretion of the investigator should any untoward effect occur. In addition, a subject may be discontinued from treatment by the investigator or the Sponsor if treatment is inappropriate, the trial plan is violated, or for administrative and/or other safety reasons. Specific details regarding procedures to be performed at treatment discontinuation are provided in Section 7.1.4 – Other Procedures.

A subject must be discontinued from treatment but continue to be monitored in the trial for any of the following reasons:

- The subject or subject's legally acceptable representative requests to discontinue treatment.
- Confirmed radiographic disease progression outlined in Section 7.1.5 (exception if the Sponsor approves treatment continuation).
- Unacceptable adverse experiences as described in Section 7.2.

- Any progression or recurrence of any malignancy, or any occurrence of another malignancy that requires active treatment
- Intercurrent illness other than another malignancy as noted above that prevents further administration of treatment
- Recurrent Grade 2 pneumonitis
- A confirmed positive serum pregnancy test
- Noncompliance with trial treatment or procedure requirements
- Investigator's decision to withdraw the subject.
- Completed 35 administrations (approximately 2 years) of treatment.

*Note: 35 administrations of study medication are calculated from the date of first dose. Subjects who stop study medication after 35 administrations may be eligible for up to 17 additional study treatments if they progress after stopping study treatment provided they meet the requirements detailed in Section 7.1.2.6.4.*

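### Section 5.8.1 ends treatment, with no agent named, for recurrent Grade 2 pneumonitis, while Table 5 stops pembrolizumab only

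*Combined protocol and SAP*

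**What the plan says.** **Recurrent Grade 2 pneumonitis.** Section 5.8.1 gives its mandatory list under "A subject must be discontinued from treatment but continue to be monitored in the trial for any of the following reasons". Recurrent Grade 2 pneumonitis is a bullet in that list, with no agent named and no reference to Table 5. Table 5, in Section 5.2.1.2.1, has a pneumonitis row for "Grade 3 or 4, or recurrent Grade 2". The instruction there is permanent discontinuation, and the column is headed "Action taken to pembrolizumab". The pneumonitis entry in Section 5.6.1 sends the reader to Table 5 for this event.

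**General rule for the combination arms.** Section 5.2.1.2 states: "If appropriate, the Investigator may attribute each toxicity event to cisplatin, 5-FU (or capecitabine) or pembrolizumab alone in the combination arms". It adds: "Pembrolizumab/placebo treatment may be interrupted or discontinued due to toxicity". The same section governs chemotherapy. It allows one chemotherapy drug to be reduced without the other, covers toxicity attributed to all three agents, and drops only the affected agent when a third modification is needed.

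**Infusion reactions.** For Grade 3 or 4, Table 9 in Section 5.6.1 says "Subject is permanently discontinued from further trial treatment administration". It gives the same outcome for Grade 2 despite premedication. Table 6, in Section 5.2.1.2.1, covers the same reactions but uses the term *study drug treatment*. "Table 3 Trial Treatments" lists cisplatin, 5-FU and capecitabine, each with the use "Comparator regimen and combination agent", beside pembrolizumab and saline.

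**The concern.** For one event the protocol gives two instructions of different scope, and the broader one is mandatory. In Arm 1 they coincide, because there is only one drug. In Arms 2 and 3 they do not. A site that obeys the 5.8.1 bullet as written stops cisplatin and the fluoropyrimidine. A site that follows Table 5 stops pembrolizumab/placebo and can keep chemotherapy going.

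What is at stake is subject care and consistency between sites. Section 4.2.2.1 presents platinum/fluoropyrimidine chemotherapy as standard first-line treatment for this disease. The literal 5.8.1 reading would withdraw it because of toxicity attributed to a different agent, and two sites could handle the same event differently while each follows the protocol.

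**Working it through.** The plan states no figure on this point, so the check compares the texts.

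| Event | Place | What is stopped, as written |
|---|---|---|
| Recurrent Grade 2 pneumonitis | 5.8.1 bullet | treatment, no component named |
| Recurrent Grade 2 pneumonitis | Table 5 (5.6.1 refers to it) | pembrolizumab |
| Infusion reaction, Grade 3-4, or Grade 2 despite premedication | Table 6 | *study drug treatment* |
| Same reaction | Table 9 | *trial treatment* |

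1. **What treatment means in 5.8.1.** The neighbouring bullets include confirmed radiographic progression, pregnancy, noncompliance and completion of 35 administrations, all of which end the whole regimen. The complete-response item in the same list counts doses of cisplatin and 5-FU or capecitabine as well as pembrolizumab. In Arms 2 and 3, then, the natural reading of the word in this section is the full combination.

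2. **What Table 5 stops.** The column heading names pembrolizumab, and the parent section is headed for pembrolizumab/placebo. Chemotherapy has its own rules in Tables 7 and 8.

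3. **Whether the two are reconciled.** Section 5.6.1 refers to Table 5, but the 5.8.1 bullet does not. Section 5.2.1.2 permits attribution to one agent, which supports Table 5, but it does not say that it overrides the mandatory list.

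4. **Whether any sentence lets chemotherapy continue.** The protocol is explicit in two related cases. Under 5.2.1.2, a subject on pembrolizumab may stop both chemotherapy drugs and stay on pembrolizumab. Under the notes to Tables 1 and 3, 5-FU or capecitabine may go on after cisplatin is capped. The reverse case, with pembrolizumab/placebo stopped and chemotherapy kept, has no such sentence.

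5. **Infusion reactions.** Table 9 is in the pembrolizumab supportive-care section, which applies to events considered related to pembrolizumab, and it is introduced as covering pembrolizumab reactions. Table 6 falls within Tables 4 to 8, so the agent-by-agent rule in 5.2.1.2 reaches it. The terms are loose, but the two tables do not contradict each other.

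6. **Who is covered.** About 750 subjects randomized 1:1:1 gives 750 × 2/3 = 500 in Arms 2 and 3. That is the number whose care the wording governs, not the number expected to have the event.

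**The case against.** The strongest reply is that the intent is recoverable. Section 5.6.1 refers the event to Table 5, Table 5 acts on pembrolizumab, 5.2.1.2 allows attribution to a single agent, and chemotherapy has separate stopping rules. A careful site would probably stop pembrolizumab/placebo only. That stands as an account of intent. It does not mend the 5.8.1 bullet, which is mandatory, unqualified and sits among whole-regimen stops. The sponsor consultation offered in 5.2.1.2 is for exceptional departures from the dose-modification tables, not from that list.

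For infusion reactions the objection largely succeeds. A reader might infer from the title of Table 3 that Table 9 orders chemotherapy stopped. A table title is not a definition, however, and the protocol also speaks of trial treatment in the Second Course Phase, where the flow chart lists only pembrolizumab. With the context in step 5, what remains is a terminology clean-up.

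A reader might also infer that the text treats the milder pneumonitis more severely than the graver, since 5.8.1 names recurrent Grade 2 but not Grade 3-4. The documents do not establish this: 5.8.1 also lists unacceptable adverse experiences, which could take in Grade 3-4 pneumonitis.

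**Conclusion.** The point holds for recurrent Grade 2 pneumonitis. The 5.8.1 bullet is broader than Table 5 and, taken literally, would withdraw cisplatin and 5-FU or capecitabine in Arms 2 and 3 for toxicity attributed to pembrolizumab/placebo. This rests on reading treatment in 5.8.1 as the assigned regimen, which the rest of its list supports. It is a low-priority correction, worth making because it is nearly free.

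Three stronger conclusions are not supported.

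- **A rate.** A reader might take a ceiling from the 39-subject gastric cohort in Section 4.3, whose listed Grade 3-5 events include no infusion reaction: 1 − 0.05^(1/39) = 0.0739 as a one-sided 95% upper limit, and 0.0739 × 250 = 18.5 subjects in one arm. That figure measures neither Grade 2 reactions despite premedication nor recurrent Grade 2 pneumonitis. The cohort also received 10 mg/kg every 2 weeks as a single agent. No rate for either event in Arms 2 and 3 can be drawn from the documents.
- **Arm 3 losing its only active therapy.** The 5.8.1 bullet applies to both blinded arms, but Arm 3 receives saline, no rate is given there, and Section 7.1.4.2 allows unblinding for subject welfare. The harm is possible but speculative.
- **An effect on the primary results.** Section 5.8.1 keeps discontinued subjects under follow-up, and Section 8.5.1 analyses efficacy by intention to treat. No effect on PFS, OS or type I error is claimed.

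**What to change.** 1. In 5.8.1, change the bullet to: *Recurrent Grade 2 pneumonitis (discontinue pembrolizumab/placebo; see Table 5)*.
2. Add to 5.2.1.2: *When pembrolizumab/placebo is permanently discontinued for toxicity attributed to it, cisplatin and 5-FU/capecitabine may continue per Tables 7 and 8 at the investigator's discretion.*
3. As a secondary clean-up, replace *study drug treatment* in Table 6 and *trial treatment administration* in Table 9 with pembrolizumab/placebo wording, in both the Grade 2 and the Grade 3-4 rows. Section 5.2.3 puts pembrolizumab/placebo ahead of cisplatin and the fluoropyrimidine, so a site facing a reaction has to decide about chemotherapy at that visit. Edits 2 and 3 make clear that the decision is the investigator's.

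The cost is a few wording edits and a short memo to sites. No new data, visits, analyses or subjects are needed.

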### **5.6.2 Supportive Care Guidelines for Cisplatin**

Prevention and/or treatment of nausea and vomiting should be managed with:

1. IV EMEND (fosaprepitant) 150 mg IV or oral EMEND (aprepitant) 3-day pack 125 mg day 1, 80 mg day 2, 80 mg day 3
2. Plus Aloxi (Palonosetron) 0.25 mg IV

Nausea may also be managed with:

1. Zofran (Ondansetron) 8 mg twice a day
2. Or Compazine (Prochlorperazine) 10 mg 3-4 times per day

Additionally, use of steroids for cisplatin associated anti-emetic support is allowed and is to follow the NCCN or institutional guidelines.

Please refer to the product label or local standards of care for additional cisplatin supportive measures.

### **5.6.3 Supportive Care Guidelines for 5-Fluorouracil**

Please refer to the product label or local standards of care for fluorouracil supportive measures.

### **5.6.4 Supportive Care Guidelines for Capecitabine**

Please refer to the product label or local standards of care for capecitabine supportive measures.

## **5.7 Diet/Activity/Other Considerations**

### **5.7.1 Diet**

Subjects should maintain a normal diet unless modifications are required to manage an AE such as diarrhoea, nausea or vomiting.

### **5.7.2 Contraception**

Pembrolizumab may have adverse effects on a foetus in utero. Furthermore, it is not known if pembrolizumab has transient adverse effects on the composition of sperm.

For this trial, male subjects will be considered to be of non-reproductive potential if they have azoospermia (whether due to having had a vasectomy or due to an underlying medical condition).

Female subjects will be considered of non-reproductive potential if they meet 1 of the following criteria:

- She is postmenopausal defined as at least 12 months with no menses without an alternative medical cause. In women < 45 years of age who are not using hormonal contraception or hormonal replacement therapy, a high follicle stimulating hormone (FSH) level in the postmenopausal range may be used to confirm a post-menopausal state. In the absence of 12 months of amenorrhea, a single FSH measurement is insufficient.
- She had a hysterectomy and/or bilateral oophorectomy, bilateral salpingectomy or bilateral tubal ligation/occlusion, at least 6 weeks prior to screening;
- She has a congenital or an acquired condition that prevents childbearing.
- Female and male subjects of reproductive potential must agree to avoid becoming pregnant or impregnating a partner, respectively, while receiving trial drug and for 120 days after the last dose of trial drug by complying with 1 of the following:
  - Practice abstinence† from heterosexual activity.

†Abstinence (relative to heterosexual activity) can be used as the sole method of contraception if it is consistently employed as the subject's preferred and usual lifestyle and if considered acceptable by local regulatory agencies and European Research Councils (ERCs)/Institutional Review Boards (IRBs). Periodic abstinence (eg, calendar, ovulation, symptothermal, post-ovulation methods, etc.) and withdrawal are not acceptable methods of contraception.

- Use (or have their partner use) acceptable contraception during heterosexual activity.

Acceptable methods of contraception area:

- Single method (1 of the following is acceptable):
  - Intrauterine device (IUD)
  - Vasectomy of a female subject's male partner
  - Contraceptive rod implanted into the skin
- Combination method (requires use of 2 of the following):
  - Diaphragm with spermicide (cannot be used in conjunction with cervical cap/spermicide)
  - Cervical cap with spermicide (nulliparous women only)

- Contraceptive sponge (nulliparous women only)
- Male condom or female condom (cannot be used together)
- Hormonal contraceptive: oral contraceptive pill (estrogen/progestin pill or progestin-only pill), contraceptive skin patch, vaginal contraceptive ring, or subcutaneous contraceptive injection

a If a contraceptive method listed above is restricted by local regulations/guidelines, then it does not qualify as an acceptable method of contraception for subjects participating at sites in this country/region.

Subjects should be informed that taking the trial medication may involve unknown risks to the foetus (unborn baby) if pregnancy were to occur during the trial. In order to participate in the trial subjects of childbearing potential must adhere to the contraception requirement (described above) from the day of study medication initiation (or 14 days prior to the initiation of trial medication for oral contraception) throughout the study period up to 120 days after the last dose of trial medication. If there is any question that a subject of childbearing potential will not reliably comply with the requirements for contraception, that subject should not be entered into the trial.

